16.3 Data Quality Control and Reporting

All procedures for the handling and analysis of data will be conducted using good clinical practices meeting ICH and U.S. FDA guidelines for the handling and analysis of data for clinical trials.

Parion Sciences will provide the study sites with secure access to and training on the EDC application sufficient to permit study site personnel to enter or correct information in the CRFs on the subjects for which they are responsible. Laboratory reports will be maintained by the site and data from central vendor transferred to data management outside the EDC system.

A CRF will be completed for each enrolled study subject. It is the investigator's responsibility to ensure the accuracy, completeness, clarity, and timeliness of the data reported in the subject's CRF. Source documentation supporting the CRF data will indicate the subject's participation in the study and will document the dates and details of study procedures, AEs, other observations, and subject status.

The investigator, or designated representative, will complete the CRF as soon as possible after information is collected. After data have been entered into the study database, a system of computerized data validation checks and manual data reviews will be implemented and applied to the database. Query reports pertaining to data omissions and discrepancies will be forwarded to

Parion Sciences, Inc.
Protocol P-321-202 Amendment 01

the clinical investigator and monitor(s) for resolution. The study database will be updated in accordance with the resolved query reports. All changes to the study database will be documented.

The audit trail entry will show the user's identification information and the date and time of any correction. The investigator will provide formal approval of all the information in the CRFs, including any changes made to the CRFs, to endorse the final submitted data for the subjects for whom the investigator is responsible. The CRF must be signed and dated by the Investigator upon subject withdrawal or completion of the study.

Parion Sciences will retain the CRF data and corresponding audit trails. A copy of the final archival CRF in the form of a CD or other electronic media will be placed in the investigator's study file.

During monitoring visits, CRFs will be reviewed by study monitor(s) for completeness, accuracy, and legibility. CRFs will be compared with the source documents to ensure that there are no discrepancies. All CRF entries, corrections, and alterations must be made by an Investigator or his/her designee. A copy of the CRF must be maintained by the Investigator.

Screen failure data will be collected in the clinical database. Minimially demographics and reason for failure will be collected for all subjects who fail to qualify for the placebo run-in period. For subjects who fail to qualify for randomization but who have entered the placebo run-in period, additional information will be collected, including demographics, ophthalmic test results for completed measurements, reason for failure to qualify for randomization, and reported adverse events

16.4 Clinical Laboratory Certification

A central clinical laboratory will be used to analyze all hematology and clinical chemistry samples in this study, with the exception of the urine pregnancy test. The investigator must maintain, on file, written evidence that the central clinical laboratory to be used is certified under the Clinical Laboratory Improvement Act or equivalent certification (depending on local regulations). Further, the investigator will maintain a copy of the certification, the range of normal values, the effective dates for the ranges, and the units of measurement for all laboratory tests requested in the protocol. If any of the laboratory measurements will be transformed and/or categorized in any way, a description of the procedures(s) used should be included. The investigator is expected to receive these documents before the shipment of clinical supplies. Publication Policy

The institution and investigators participating in this trial shall have no rights to publish, disclose or present the results of this study without prior written consent of Parion Sciences, Inc.

APPENDIX I: SCHEDULE OF VISITS AND PROCEDURES.

	Visit 1	Phone call	Visit 2	Phone Call	Visit 3	Phone call	Visit 4	ET	Follow up
Event	Screening Visit Day -14	Day -7 ± 1 to Day 1	Randomization -Treatment Day 1	Day 8 ± 1	Treatment Day 15	Day 22±	Day 29	Early Termination Visit	Follow up call 7 days ± 2 after Visit 4
Informed Consent	X								
Eligibility criteria reviewed	X		X						
Medical History/Changes	X		X		X		X	X	X
Concomitant Medication/Changes	Xª		X		X		X	X	X
Abbreviated Physical Exam	X						X	X	
Vital Signs	X		X		X		X	X	
Urine Pregnancy Test	X						X	X	
Serum Chemistry, Hematology	X				X ^b		X	X	
Dry Eye Symptoms ^c	X		X		X		X		
Study Medication Instillation Technique Training/Observation in Clinic	X ^d		Xe		Xe				
Dispense Study Medication	X ^d		Xe		Xe				
Drop Instillation Comfort Assessment ^f	X		X		X				

Page 62

CONFIDENTIAL

	Visit 1	Phone call	Visit 2	Phone Call	Visit 3	Phone call	Visit 4	ET	Follow up
Event	Screening Visit Day -14	Day -7 ± 1 to Day 1	Randomization -Treatment Day 1	Day 8 ± 1	Treatment Day 15	Day 22±	Day 29	Early Termination Visit	Follow up call 7 days ± 2 after Visit 4
Subject reminder for when to take medication		X		X		X			
Collect Returned Study Medication			X ^d		Xe		Xe	Xe	
Best Corrected Visual Acuity	X		X				X		
Biomicroscopy and External Eye Examination	X		X		X		X	X	
Tear osmolarity & Meibomian gland assessment ^g	X								
Tear Collection for Biomarker ^h			X		X		X		
TBUT	X		X		X		X		
Corneal Staining	X		X		X		X		
Bulbar Conjunctival Staining	X		X		X		X		
Lid wiper staining of the upper eyelid ⁱ	X		X		X		X		
Impression Cytology ^j			X				X		
Schirmer's Test (unanesthetized)	X								
Intraocular Pressure	X								
Adverse Event Monitoring	X	X	X	X	X	X	X	X	X

Concomitant medications taken within 28 days of screening will be reviewed Only serum potassium

Protocol P-321-202 Amendment 01

- c. Dry eye symptom questionnaires (SANDE, SPEED, and 7-item symptom questionnaire) will be completed as ordered before any other study assessments are performed at each visit. SANDE Part 1 will be completed at Visits 1-4, and Part 2 will be completed at Visits 2, 3, and 4.
- d. Placebo run-in study medication only
- e. Double-masked study medication per assigned subject treatment number
- f. To be assessed within 5 minutes after dosing in clinic for the Fellow Eye only
- g. Meibomian gland assessment to include clinical gland evaluation ± meibography (if available). If available, photographs will become part of the source and electronic data.
- h. Must be completed before any ocular staining has occurred. Tears from the Study Eye for prostaglandins and from the Fellow Eye for MMP-9 activity
- i. Lid wiper staining may include photographs if technology is available. If available, photographs will become part of the source and electronic data.
- j. Must be conducted after corneal, conjunctival and lid wiper staining and will be done in the Study Eye only

APPENDIX II: ADVERSE EVENT REPORTING

Adverse Event Definitions

Adverse Event (AE): Any untoward medical occurrence in a subject or clinical investigation subject administered a pharmaceutical product; which does not necessarily have a causal relationship with this treatment.

Treatment Emergent Adverse Event (TEAE): A treatment emergent AE (TEAE) is an AE that either commenced following initiation of study treatment or was present prior to study treatment but increased in frequency or severity following initiation of study treatment.

An SAE is any adverse drug experience occurring at any dose that results in any of the following outcomes:

- Death
- A life-threatening adverse drug experience (i.e., the subject is at immediate risk of death at the time of the event)
- In-patient hospitalization or prolongation of existing hospitalization
- A persistent or significant incapacity or substantial disruption of the ability to conduct normal life functions
- A congenital anomaly/birth defect
- Important medical events that may not result in death, be life-threatening, or require hospitalization may be considered serious when, based upon appropriate medical judgment, they may jeopardize the subject and may require medical or surgical intervention to prevent one of the outcomes listed in this definition

A **NON-SERIOUS ADVERSE EVENT** is any adverse event that does not meet the definitions for serious adverse events as described above.

Adverse Event Classification

Each **Adverse Event** will be classified as **SERIOUS** or **NONSERIOUS** using the definitions provided above.

The INTENSITY of each Adverse Event will be classified as MILD, MODERATE, or SEVERE.

The CAUSALITY of the Adverse Event will be classified as NOT RELATED to study medication, POSSIBLY RELATED to study medication, or RELATED to study medication defined as follows:

Not related: An event that does not follow a reasonable temporal sequence from

administration to the suspected drug, is not a known response pattern to

the suspect drug or due wholly to the subject's clinical state or other factors.

Possibly related: An event that follows a reasonable temporal sequence form administration

of the study medication, follows a known or expected response pattern to the suspected drug, but that could be explained by the subject's clinical

state or other factors.

Related: An event that follows a distinct temporal sequence from administration of

the study medication, follows a known or expected response pattern to the suspected drug, and cannot be explained by subject's clinical state or other

factors

The investigator will classify the study drug action taken with regard to the AE. The action taken will be classified according to the categories shown below.

Classifications for Study Drug Action Taken with Regard to an AE

Classification	Definition		
Dose not changed	Study drug dose not changed in response to an AE		
Drug interrupted	Study drug administration interrupted in response to an AE		
Drug withdrawn	Study drug administration permanently discontinued in response to an AE		
Not applicable Action taken regarding study drug administration does not apply.			
	"Not applicable" will be used in circumstances such as when the investigational treatment had been completed before the AE began and no opportunity to decide whether to continue, interrupt, or withdraw treatment is possible.		

An AE will be followed until the investigator has determined and provided the final outcome. The outcome will be classified according to the categories shown below.

Classifications for Outcome of an AE

Classification	Definition
Recovered/Resolved	Resolution of an AE with no residual signs or symptoms
Recovered/Resolved With Sequelae	Resolution of an AE with residual signs or symptoms
Not Recovered/Not Resolved	Either incomplete improvement or no improvement of an AE, such that
(Continuing)	it remains ongoing
Fatal	Outcome of an AE is death. "Fatal" will be used when death is at least possibly related to the AE.
Unknown	Outcome of an AE is not known (e.g., a subject lost to follow-up)

The investigator ensures adequate medical care is provided to subjects for any AEs, including clinically significant laboratory values related to study drug. In addition, the investigator will describe whether any treatment was given for the AE. "Yes" is used if any treatment was given in response to an AE, and may include treatments such as other medications, hospitalization, surgery, or physical therapy. "No" indicates the absence of any kind of treatment for an AE.

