3.3 Clinical Experience with P-321 Ophthalmic Solution

There has been one study completed with P-321 Ophthalmic Solution in which 40 subjects with mild to moderate dry eye disease were treated with P-321 Ophthalmic Solution (Protocol P-321-101). In this study, P-321 Ophthalmic Solution was well-tolerated at concentrations of 0.0005%, 0.0015%, 0.005% instilled twice daily for up to 15 days and 0.01% instilled twice daily for up to 28 days. There were no clinically relevant adverse drug-related, dose-related or time of treatment-related effects on any safety measure. No serious adverse events (SAEs) were reported. No evidence of systemic exposure of P-321 was observed.

Although the above study was not powered for effects on efficacy measurements, improvements in the frequency and severity of symptoms of dry eye disease that approached statistical significance compared with placebo were observed. In addition, consistent with the proposed mechanism of action of P-321, the treatment difference relative to placebo favored P-321 for the measurements of tear meniscus height observed in this study.

Additional details regarding the clinical and nonclinical experience with P-321 Opthalmic Solution can be found in the Investigator's Brochure.

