A Treatment-related AE is any adverse event reported on the CRF that is marked as being Related or Possibly Related to the study medication. Additionally, it is assumed that an AE without a relationship is a Treatment-related AE.

Concomitant Medications for Placebo Run-in Period

Concomitant medications for the placebo run-in period are those medications taken during the placebo run-in period.

Concomitant Medications for Double-Masked Period

Concomitant medications for the double-masked period are those medications taken while on the double-masked period study treatment.

Previous Medications for Placebo Run-in Period

Previous medications for the placebo run-in period are those medications that ended prior to the initiation of the placebo run-in period study treatment.

Previous Medications for Double-Masked Period

Previous medications for the double-masked period are those medications that ended prior to the initiation of the double-masked period study treatment.

Study Eye

If a subject has only one qualifying eye, that eye will be the Study Eye. If both eyes of the subject qualify, then the Study Eye will be the eye with the highest total corneal staining score. If the scores for total corneal staining are the same, the Study Eye will be the right eye.

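### The AE causality scale offers no related grade for a well-timed reaction that is neither known nor expected for P-321

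*Protocol*

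**What the plan says.** Protocol Appendix II has three grades: "The CAUSALITY of the Adverse Event will be classified as NOT RELATED to study medication, POSSIBLY RELATED to study medication, or RELATED". Their conditions are:

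- **Possibly related:** reasonable timing, and the event "follows a known or expected response pattern to the suspected drug, but that could be explained by the subject's clinical" state or other factors.
- **Related:** distinct timing relative to "the study medication, follows a known or expected response pattern to the" drug, and no other explanation.
- **Not related:** three grounds in one sentence. The first is the lack of reasonable timing. The second is that the event "is not a known response pattern to" the drug. The third follows the word 'or': "the suspect drug or due wholly to the subject's clinical state or other factors".

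SAP 3.3.7 defines a treatment-related AE as "any adverse event reported on the CRF that is marked as being Related or Possibly Related to the study medication", and adds that an event with no relationship recorded is also counted. SAP 5.3.1 gives a missing relationship the strongest grade. The outputs are Tables 14.3.1.3.1 (double-masked period) and 14.3.1.3.2 (run-in), plus the by-relationship summary in SAP 5.3.1 and Protocol 11.5.

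On prior human experience, Protocol 3.3 reports "one study completed with P-321 Ophthalmic Solution in which 40 subjects with mild to moderate dry eye disease were treated". The highest regimen was 0.01% twice daily for up to 28 days, and no clinically relevant drug-related effect was found. I found no other causality rule in either document.

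**The concern.** Both related grades require the event to match something already known or expected. Timing and the lack of any other cause cannot substitute for that match. An investigator who sees a clear reaction after dosing, of a kind nobody anticipated, cannot record it as even possibly related and still follow Appendix II.

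The grade then passes unchanged into the related-AE tables. Safety and tolerability are among the secondary objectives in the synopsis, and are the secondary objective in Protocol 4 and SAP 2. The plan's handling is also uneven: a blank relationship counts as related, whereas a well-timed novel reaction graded by the definitions does not. Sites that follow the text and sites that use their own judgement would grade the same event differently.

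**Working it through.** The plan gives no figure to reproduce. The check is to run every type of event through the three definitions.

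**Inputs (Appendix II).** Timing: none, reasonable or distinct. Pattern: known or expected, or novel (neither). Other explanation: none, could explain, or wholly explains. That gives 3 × 2 × 3 = 18 combinations, 9 of them novel.

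**Two readings of Not related.** Let A be no reasonable timing, B no known pattern, and C wholly due to other factors. The loose punctuation allows (A or B or C), or ((A and B) or C).

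The 3 novel combinations without plausible timing are Not related on both readings, which is unobjectionable. The other 6 come out as follows:

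| Timing | Other explanation | Possibly related | Related | Not related: A or B or C | Not related: (A and B) or C |
|---|---|---|---|---|---|
| reasonable | none | no | no | yes | no |
| reasonable | could explain | no | no | yes | no |
| reasonable | wholly explains | no | no | yes | yes |
| distinct | none | no | no | yes | no |
| distinct | could explain | no | no | yes | no |
| distinct | wholly explains | no | no | yes | yes |

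- Neither reading gives any of the 6 a related grade.
- With the grounds as alternatives, all 6 are Not related.
- On the joint reading, the 2 wholly explained by other factors are Not related, and the other 4 fit no category.
- Not related is the right answer for the 2 wholly explained cases. The defect is in the other 4.

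**What reaches the tables (SAP 3.3.7).** Entered as Not related: omitted from 14.3.1.3.1 and 14.3.1.3.2. Left blank because nothing fits: counted as related, at the strongest grade. The same event can therefore land at either extreme.

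**How thin the known pattern is.** These figures are context; the gap itself does not depend on them.

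- Daily amount per eye relative to the highest earlier regimen, assuming one drop per dose of equal size: (0.017 × 3)/(0.01 × 2) = 0.051/0.020 = 2.55.
- Chance that a reaction of true incidence p appeared in none of 40 subjects: (1 − p)^40. The incidences are my assumptions. At p = 2%, 0.98^40 = 0.446. At p = 5%, 0.95^40 = 0.129.
- The 40 subjects were spread over four concentrations, so for a dose-dependent reaction these chances would be higher.

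**The case against.** The strongest reply is that the gap is narrow and does little damage. Most of it stands.

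- **Expected reactions are covered.** A reader might infer that anything not yet seen in humans must be graded Not related. The text does not support that, because the criterion also admits expected patterns. Dose-dependent ocular irritation from toxicology (Protocol 3.2.3) and potassium effects of an ENaC inhibitor (Protocol 7.11) can still be graded related. The Investigator's Brochure, which may widen what counts as expected, is not available here. It follows that (1 − p)^40 is the chance of a reaction going unseen in the earlier study, not the chance that it is neither known nor expected.
- **Detection does not rest on the grade.** A reader might infer that the trial is blind to new reactions. It is not. Such events stay in the all-TEAE, severity, serious and discontinuation summaries by arm and in the listings, so the randomized comparison is intact. Serious events are reported within 24 hours whatever the causality (Protocol 10.1.1), and neither withdrawal (6.5) nor study termination (15.2) is tied to the grade.
- **Many misgraded cases are not demonstrated.** The documents give no incidence for an unanticipated reaction. A common one would probably have appeared already: at an assumed 10%, 0.9^40 = 0.015, unless it depends strongly on dose.
- **A flat Not related is not certain.** On the joint reading there is no category, and a blank is then counted as related.

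None of this supplies a route to a related grade for the 4 combinations in question. The blank rule does not help once Not related has been entered.

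**Conclusion.** The point holds as a defect in the causality definitions. A well-timed reaction that is neither known nor expected, and not wholly due to other causes, cannot be graded Possibly related or Related on either reading. The consequence is understated or inconsistent labelling in Tables 14.3.1.3.1 and 14.3.1.3.2 and in the by-relationship summary. AE incidence by arm is not biased.

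The number of events affected cannot be estimated from the documents. The conclusion rests on the wording of Appendix II and on investigators applying it as written. The repair is worth making because earlier human experience is one study of 40 treated subjects at lower daily amounts, so few human reaction patterns are established. I am confident about the wording gap, and expect its practical effect to be modest.

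**What to change.** In Appendix II:

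1. Define Possibly related by reasonable timing and a drug cause that cannot be excluded, even if the subject's condition could also explain the event. Drop the pattern as a requirement.
2. Remove the absence of a known pattern as a ground sufficient on its own for Not related, and punctuate the remaining grounds so that only one reading is possible.
3. For Related, treat the pattern as supporting evidence and not as a condition.

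The 4 problem combinations then reach at least Possibly related, and the 2 wholly explained by other factors stay Not related. The SAP 3.3.7 definition needs no change.

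This is a wording amendment with no new data. The cost is lower specificity. With TID dosing for 28 days, most on-treatment events have plausible timing, so more events, including background ones, will be graded Possibly related in both arms. The documents do not allow that increase to be sized. Grading in the double-masked period is done under masking, which limits differential grading between arms.

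If grading is already complete, have Not related events with plausible timing reviewed before unmasking, and state the limitation in the study report.

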APPENDIX III: INSTILLATION OF MEDICATION

At Screening Visit 1, study personnel will instruct subjects who are eligible to proceed into the single-masked placebo run-in period on how to instill medication into their eyes using the study medication that subjects will be taking home. At subsequent Visits 2 and 3 after all in clinic assessments have been completed, study personnel will observe the subject's technique in self-instilling study medication using new supplies dispensed at these visits. As necessary, study personnel will re-instruct the subject on proper instillation technique and reinforce the importance of taking study medication three times daily.

Instillation Technique

- Open a pouch and remove the vial. Both eyes will be dosed with that vial
- Subject should slightly tilt his/her head back and look upward
- The subject should gently squeeze the bottle allowing one drop to coat the ocular surface on the right eye.
- Repeat instruction for left eye using the same bottle.
- The subject should gently close his or her eyes for a few seconds.
- Recapp the used vial, place it back into its pouch, and return it to the clinic for later reconciliation.

Within 5 minutes following instillation of study drops, subject should complete the Drop Instillation Comfort Assessment (Appendix VI) for the fellow eye only.

